6.3.5 Study Visits

See Appendix 3

6.3.6 End of Study and Follow Up

At the end of the study, all participants in each group (TAU, iCanCope, iCanCope+CM) will be required to complete the identical set of assessments at intake, minus demographic information. Individuals who prematurely left early or who withdrawn from the study will not be asked to complete the end of the study survey. Additionally, individuals with access to the iCanCope mobile application license will end and will not be able utilize the mobile application until the follow-up is complete. For individuals who did not have access to the iCanCope mobile application they will continue not having access to the mobile application.

All participants in each group will complete a 6-week post discharge follow-up. The follow-up will be identical to the discharge evaluation. Individuals will be emailed a secured email by the research assistant to complete the survey one day before the 6-week survey. All participants will have a one-week (7days) to complete the assessment, and a reminder email will be sent on the last day of the survey to the participants. Individuals will not be required to complete but will be encouraged to do so.

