iCanCope-NF & CM Group: In addition to the *iCanCope-NF* activities outlined above, individuals will be rewarded with incentives such as points that are redeemable for prize-based gift card vouchers.[i] (#_edn1) Points will be accrued through access to new sections, daily check-ins, and engagement of the mobile application. Based on research, the total amount of money that can be earned by the patient over the course of the two months is 50 dollars USD. Individuals who are only randomized in the ICC-CM condition earn from \$1 to \$5 dollar amazon gift card per week for eight weeks (based on their usage). With an additional \$10 dollar gift card, if they check in every day. The total of the incentives can reach up to 50 dollars.

Control Group: The control group is designed to assess for potential effects on outcomes of time, attention, during the study. In addition to usual care, participants will be required to complete baseline and follow-up assessments similar to that of the intervention groups. They will be given that patient education, through preapproved flyers and information found from national websites regarding pain management, but no self-management strategies or opportunities for social support. They will not have access to the mobile application during the course of experiment; however, the control group will be offered the full *iCanCope-NF* program following the trial (T2) for a period of 2 months after the study is over.

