6.2 Assessments

6.2.1 Efficacy

All psychometric measures (see appendix) will be evaluated at intake, discharge, follow-up. All of these measures have evidence of reliability and validity in adults in this age range and include target specific measures of NF1 have recommended in previous trials. The **primary research** question is what is the feasibility of the *iCanCope-NF* program? We define feasibility as (1) rates of accrual and dropout, daily logins, engagement, and outcome measures completed and (2) perceptions regarding intervention acceptability and satisfaction; and what are the levels of engagement. logins, with the intervention? The **secondary questions** are: (1) how does the *iCanCope-NF* program compare with the control condition in differences of pain and pain-related activity limitations, sleep functioning, emotional functioning (depression, anxiety), opioid usage, pain catastrophizing, self-efficacy, respondent burden (i.e. Physical Functioning, R, Vitality, Social Functioning, Role-Emotional, and Mental Health), and psychological flexibility immediately post-treatment (T2), (2) does the *iCanCope-NF + CM* increase the engagement of the *iCanCope-NF* program as compared to *iCanCope-NF* without CM, and do their corresponding levels of pain and pain-

related activity decrease with CM?, and (3) do individuals with NF1 utilize the MBAA to help reduce pain symptoms? We hypothesize that by customizing and including MBAA to the program for adults with NF1, that individuals who engage regularly as seen through Analytics Platform for Evaluating Effective Engagement (APEEE) application, will acquire new sets of skills to facilitate pain management, while pain as reported with the Brief Pain Inventory will decrease.

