7.6 Data Quality Assurance

The PI is responsible for monitoring of quality control and assurance through regular communication with the research team via bi-weekly meetings. The PI will train the research assistant on ensuring consistent and reliable methods of recruitment, data management, and training sessions through initial trainings. Additionally, the PI will provide in situ training to the research assistant throughout the research experiment. A standard operating procedure (see appendix) will be implemented and trained on.

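### GAD-7 items coded 1–4 give totals of 7–28, which do not fit the printed bands (1–21) or the exclusion cut-off of 5; secondarily, no visible step has repeat mood scores read promptly

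*Combined protocol and SAP*

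**What the plan says.** **GAD-7 scoring.** The Synopsis and 5.2.2 give four response options per item, numbered 1 (not at all sure) to 4 (nearly every day), and sum them. The bands printed for the total are minimal 1–4, mild 5–9, moderate 10–14 and severe 15–21. Section 5.3.2 excludes candidates whose GAD-7 is 5 or more, or whose PHQ-9 is 10 or more.

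**Repeat assessment.** Section 6.2.1 states: "All psychometric measures (see appendix) will be evaluated at intake, discharge, follow-up". Section 6.3.6 repeats the intake set at discharge, without demographics, and says of the 6-week assessment: "The follow-up will be identical to the discharge evaluation". It is delivered by email ("Individuals will be emailed a secured email by the research assistant to complete the survey one day before the 6-week survey") with seven days to respond, and it is voluntary: "Individuals will not be required to complete but will be encouraged to do so".

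**What can be done with a worrying score.** Section 6.3.7 commits staff to recommend medical contact, and to help find care, when a participant deteriorates psychologically. It names no score, reader or time limit. Survey data are open to the principal investigator only (7.8). That investigator's safety reviews are monthly in 7.12 but at least quarterly, and after any serious adverse event, in 7.11. Section 6.2.3 has the investigator ask about adverse events at each visit. Section 6.3.1 counts follow-up as one of three virtual visits, but lists a 15-minute debriefing at discharge only.

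**What cannot be seen.** Section 6.3.5 on study visits reads only "See Appendix 3", and 7.6 says "A standard operating procedure (see appendix) will be implemented and trained on". Neither attachment is in the supplied text.

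**The concern.** The GAD-7 serves both as an entry criterion and as a secondary outcome. If the item codes are followed as printed, the entry rule admits nobody. The outcome bands are also displaced: the lowest is empty, and the most anxious respondents fall above the top one. Anyone who builds the survey score or the analysis file from 5.2.2 has two incompatible instructions and must choose between them.

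The second matter is smaller. The plan collects anxiety scores after treatment, and promises a response to psychological deterioration, but the visible text does not connect the two. The link looks thinnest at the emailed 6-week survey, for which no live contact is described. A 6.3.7 action prompted by a score cannot begin until someone has read that score.

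**Working it through.** **Inputs.** Item codes 1–4 and the four bands (5.2.2 and Synopsis); exclusion at 5 or more (5.3.2). The number of items, 7, is taken from the instrument's name and agrees with the printed maximum, since 21 / 3 = 7.

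**Step 1: try to reproduce the printed range.** Minimum = 7 × lowest code; maximum = 7 × highest code.
- Codes 1–4: 7 × 1 = 7 to 7 × 4 = 28. This does not reproduce the printed 1–21.
- Codes 0–3: 7 × 0 = 0 to 7 × 3 = 21. This reproduces the printed maximum.

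**Step 2: which printed scores can occur.**

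| Band | Codes 1–4 | Codes 0–3 |
|---|---|---|
| minimal 1–4 | 0 of 4 | 4 of 4 |
| mild 5–9 | 3 of 5 (7–9) | 5 of 5 |
| moderate 10–14 | 5 of 5 | 5 of 5 |
| severe 15–21 | 7 of 7 | 7 of 7 |
| possible totals with no band | 22–28 | 0 |

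**Step 3: what the printed cut-offs mean.** Moving every item by 1 moves the total by 7, so the equivalent on 0–3 coding is the printed value minus 7: 5 − 7 = −2, 10 − 7 = 3, 15 − 7 = 8. A person labelled moderate at 10 would have only 3 on 0–3 coding. Totals of 22–28 correspond to 15–21, which is the whole of the severe band.

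**Step 4: eligibility.** The lowest possible total on 1–4 coding is 7, and 7 ≥ 5, so every completed form meets the exclusion. On 0–3 coding, totals of 0–4 pass.

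**Step 5: timing of the secondary point.** Follow-up falls at week 8 + 6 = 14 and can be returned up to 7 days later, so by about week 15. If the safety reviews include individual scores, which the text does not say, the longest wait is 365.25 / 12 = 30.4 days under 7.12 or 365.25 / 4 = 91.3 days under 7.11. If they do not, the visible text sets no limit. The principal investigator may read sooner in either case.

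**Step 6: is the PHQ-9 repeated?** The GAD-7 is a named outcome, so its repetition is explicit. Repetition of the PHQ-9 is inferred: intake measures are repeated (6.2.1, 6.3.6), depression is compared at T2 (6.4.3.2), and the PHQ-9 is the only depression scale that the visible text names (5.3.2, 7.7). Its item codes are not given, so its cut-off of 10 could not be checked in the same way.

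**The case against.** **On the scoring.** The bands and the maximum of 21 plainly suit 0–3 coding, so this may be a slip of description and the survey may be scored correctly. That is fair. A reader might infer that the trial would in practice turn everyone away; the documents do not show this, because they do not say how the survey computes the total. What stands is that the text is wrong as written in two places, and that an entry rule depends on it.

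A reader might also infer that no GAD-7 cut-off can work until the items are recoded. That goes too far. A cut-off raised by 7 (12 in place of 5, or 17 in place of 10) would work on 1–4 coding, and so would a change-from-baseline rule. It is the printed cut-offs that fail.

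**On reading the scores.** A tempting stronger reading is that nobody looks at the scores and that live contact is over by follow-up. The documents do not establish either. Follow-up is nominally a visit, so the adverse-event inquiry in 6.2.3 applies on its face, and 6.3.6 equates it with discharge, which has a debriefing. Against that, 6.3.1 allots follow-up only 30 minutes, for assessments, and 6.3.6 describes an emailed survey. The ambiguity cannot be settled from the text, and Appendix 3 or the operating procedure may hold a rule.

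Nor should the loss of in-app emergency information be overstated. For the two app arms, 6.3.6 says the "license will end and will not be able utilize the mobile application until the follow-up is complete". For controls the text is unclear, since 6.1.1 offers the app "following the trial (T2) for a period of 2 months after the study is over" while 6.3.6 continues their lack of access. But the examples in 6.1.5 are public emergency services, a national hotline and primary care, all reachable without the app. What the app arms lose is the personally tailored contacts in 6.3.7.

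Finally, 7.12 classes the study as minimal risk and entry screens out elevated scores, so few cases are expected. Any threshold or response time would be a policy choice that the documents do not dictate. These arguments reduce the second point to an optional suggestion.

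**Conclusion.** The scoring point holds and should be corrected. As printed, a completed GAD-7 runs from 7 to 28, 100% of respondents meet the exclusion cut-off, one band is empty and seven possible totals (22–28) have no label. The only assumption is that the instrument has seven items, which its name and the printed maximum both support.

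The safety point is secondary and conditional. The visible text does not require repeat scores to be read promptly so that 6.3.7 can be applied. The 30-to-91-day range rests on the unconfirmed assumption that safety reviews include scores, and the whole point falls away if an unseen appendix covers it.

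**What to change.** **Scoring (should be done).** In the Synopsis and 5.2.2, code the items 0 (not at all sure) to 3 (nearly every day), giving a total of 0–21, and start the lowest band at 0 (0–4). In 5.3.2, state that the cut-off of 5 uses this scoring. Confirm that the survey computes the total in this way. The cost is a wording change with no new data; any complete form already scored on 1–4 coding converts by subtracting 7.

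**Reading repeat scores (optional).** If Appendix 3 or the operating procedure already sets a rule, cite it in 6.3.6. If not, have the principal investigator, who already holds sole survey access under 7.8, open each returned discharge and follow-up survey promptly, apply 6.3.7 where scores show deterioration from baseline, and log each contact by arm. State in 6.3.1 that such contact is allowed despite the bar on other communication, and settle whether safety reviews are monthly or quarterly.

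This takes some of the principal investigator's time. If 108 participants reach discharge and all return the follow-up, there are 108 + 108 = 216 surveys to open, or 216 / 18 = 12 a month averaged over the 18 months, and rather more once discharges begin. There are two other downsides. The principal investigator, who also runs the analysis (6.4.1), would see scores during the trial, whereas 7.5 describes automatic monitoring that withholds data that could influence the outcome. A few extra contacts before the 6-week outcome could also differ between arms, which is why they should be logged.

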6.3.7 Removal of Subjects

In cases of psychological deterioration, we will recommend to patients to contact their physician immediately and consider withdrawing from the study to receive more intensive treatments. When necessary subjects will be withdrawn from this study and research staff will assist patients with appropriate sites for treatment such a physician, crisis center, or emergency room. The mobile application will also have emergency information available that can be tailored by each patient to provide specific contacts that they may need. In instances of suicidal or homicidal risk, appropriate authorities including their primary provider will be informed and necessary actions (seeking crisis/suicidality evaluations and possible hospitalization) taken.

6.4 Statistical Method

6.4.1 Statistical Design

Statistical procedures and models have been selected according to the research questions being investigated and the types of data available. We will use $\alpha < .05$ but will use appropriate corrections for multiple tests. Statistical analyses will be conducted by principal investigator using SPSS, SAS, or R with consultation from the coinvestigators. Using logistic regression for categorical and ANOVA for continuous measures, we will conduct preliminary analyses of the adequacy of the randomization procedure, the comparability of baseline measures across conditions, and the possible need for covariates in the analyses of treatment outcome data.

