6.1.2 Method of Assignment/Randomization

Participants will be randomized to one of the three conditions using an urn randomization algorithm which modifies ongoing randomization probabilities based on prior group composition groups, and controls for other predictive factors. This process greatly reduces experimenter bias and other internal validity threats to integrity. Gender be the only variable

that will be attempted to controlled for to ensure equal representation across the groups within the urn randomization using stratification.

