6.4.2 Sample Size Considerations

An a priori power analysis conducted through G*Power (Universität Kiel, v. 3.1.9.2) estimated a conservative sample size analysis for the RCT. We are expecting a total of 140 participants, given the length of the trial, we estimate 20% attrition rate of the final sample, giving us a total sample of (n=36) per group, for a final sample size of 108. The power analysis is based on previously utilized research in which estimated effect sizes ranged from 20 to 40 individuals per group (52). We will attempt to enroll equal numbers of male and female individuals to evaluate gender differences through urn randomization process.

52. Hancock, G. R. and R. O. Mueller, Eds. (2010). *The Reviewer's Guide to Quantitative Methods. Power Analysis*. New York, NY, Routledge.

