6.4.4 Subsets and Covariates

N/A

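### Covariate choice is tied to between-arm baseline comparisons and Section 6.4.4 says N/A; baseline score and gender should be named as fixed covariates

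*Combined protocol and SAP*

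**What the plan says.** Section 6.4.1, repeated in 6.4.3, plans preliminary analyses by logistic regression (categorical measures) and ANOVA (continuous measures). They have three purposes: whether randomisation worked, whether the arms are comparable at baseline, and "the possible need for covariates in the analyses of treatment outcome data". No selection threshold and no list of candidate covariates is given.

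Under "6.4.4 Subsets and Covariates" the only entry is N/A.

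Section 6.1.2 describes an urn randomisation with stratification: "Gender be the only variable" to be controlled in it.

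Sections 6.2.1 and 6.3.6 have the same instruments completed at intake, discharge and follow-up, so most questionnaire outcomes have an intake value. Section 5.2.1 describes the two pain outcomes as within-group change. Section 6.4.3.2 plans an estimating-equation approach for the app-versus-control comparison. Neither 6.4.3.1 nor 6.4.3.2 names the intake score or gender as an adjustment term. Gender appears as an analysis variable only in the module-use analysis of 6.4.3.3.

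**The concern.** Two things are wrong. First, the sections disagree: 6.4.1 and 6.4.3 leave covariates to be settled from the data, and 6.4.4 says the matter does not apply. If N/A means only that nothing is pre-specified, the choice is still open.

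Second, a between-arm comparison of baseline measures is the wrong guide. Under randomisation any difference is chance. A covariate earns its place by predicting the outcome, and a balance test says nothing about that. If selection used a 5% test, a given covariate would enter in about 1 trial in 20, so precision would stay close to that of an unadjusted analysis however prognostic the intake score is.

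At stake are precision in a trial with only 36 per arm, and discretion. The principal investigator conducts the analysis (6.4.1) and is the only person with access to the survey data (7.8), so the covariate set can be chosen after outcomes are visible.

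**Working it through.** **The plan's own figure.** Section 6.4.2 arrives at 36 per group and 108 in total. This cannot be reproduced: no effect size, SD, power or test is stated, and where an effect size should stand the text has "estimated effect sizes ranged from 20 to 40 individuals per group". Working backwards, 36 per arm gives 80% power in a two-arm comparison at d = (1.96 + 0.84) × √(2/36) ≈ 0.66. That is an implied value, not the plan's.

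**Inputs from the documents.** 36 per arm (6.4.2); alpha 0.05 before a multiplicity correction that is not specified (6.4.1); intake scores collected (6.2.1); pain outcomes expressed as change (5.2.1).

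**Assumed inputs, because the documents give none.** Two-sided test; d = 0.5; SD = 1 at both times; baseline-to-post correlation r = 0.3, 0.5 or 0.7; selection at p < 0.05 in a three-arm baseline ANOVA.

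**Closed form.** Power ≈ Φ( d / (s√(2/n)) − 1.96 ), with √(2/36) = 0.2357 and 0.5/0.2357 = 2.121. The residual SD s is:
- post score only: s = 1, so Φ(2.121 − 1.96) = 56%
- change score: s = √(2(1 − r)) = 1.183, 1.000, 0.775, giving 43%, 56%, 78%
- ANCOVA: s = √(1 − r²) = 0.954, 0.866, 0.714, giving 60%, 69%, 84%

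In sample-size terms at r = 0.5, ANCOVA with 36 per arm is worth 36/(1 − 0.25) = 48 per arm unadjusted. For 80% power at d = 0.5 it needs 48 per arm, against 63 for either unadjusted form.

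**Simulation of the selection rule.** The rule is: adjust for baseline if the baseline ANOVA has p < 0.05, otherwise analyse unadjusted. With 6,000 runs per scenario:

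| r | Planned ANCOVA | Rule, post score | Gain | Rule, change score | Gain |
|---|---|---|---|---|---|
| 0.3 | 59% | 56% | 3 | 43% | 16 |
| 0.5 | 68% | 57% | 11 | 55% | 13 |
| 0.7 | 83% | 57% | 26 | 78% | 5 |

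Gains are in percentage points, from the rounded figures. A repeat with 40,000 runs agreed with every power entry to within about one point.

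**Type I error.** On post scores the rule gave 5.1%, 4.4% and 4.2% at r = 0.3, 0.5 and 0.7 (8,000 runs). ANCOVA throughout gave 4.9% to 5.2%.

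**Gender.** If gender explains 1% to 5% of outcome variance (assumed), adjusting for it alone moves power from 56% to between 57% and 59%.

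**The case against.** Several stronger readings are tempting, and the documents do not support them.

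- *The plan excludes baseline score and gender from its models.* It does not say so. The estimating-equation approach in 6.4.3.2 could treat intake as one of the repeated measures, which would recover part or all of the gain. The same section mentions unnamed trait-level characteristics in interaction terms. The supportable statement is that adjustment is unspecified.
- *The plan lets a significance test decide.* Section 6.4.1 lists the need for covariates as one purpose of the preliminary comparisons, without a threshold or decision rule. The p < 0.05 rule above is an assumption used to attach a size.
- *The loss is 26 points.* That holds only at r = 0.7 and against post scores alone. Section 5.2.1 names change, which already uses the baseline; against change scores the gap at r = 0.7 is about 5 points. The case is not uniformly weaker, though: at r = 0.3 the change score does worse than the post score.
- *False positives rise.* They do not; the rule is at most slightly conservative.
- *Omitting gender throws away power.* The effect is 1 to 3 points under the variance shares assumed.

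Scope also matters. App minutes and satisfaction have no intake value. Section 6.2.1 makes feasibility the primary question and the app-versus-control comparison secondary, and this is a pilot. The eligibility cut-offs on BPI interference and GAD-7 (5.3.2) restrict the baseline range and may lower r for those scales.

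What remains is the conflict between sections, a selection guide unrelated to precision, and models that do not say how intake scores are used. Pilot status lowers the stakes but does not remove them: Section 4.2 makes pain reduction the primary objective.

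**Conclusion.** The point holds as a pre-specification gap with a probable cost in precision. Sections 6.4.1 and 6.4.3 conflict with 6.4.4, and no between-arm outcome model names baseline score or gender as an adjustment term.

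For questionnaire outcomes with an intake value, planned ANCOVA gains about 3 to 26 points of power over baseline-test selection on post scores, and about 5 to 16 points over the same rule on change scores. The direction was the same at every correlation tried. The size rests on assumed d, r and selection threshold, and would shrink if intake is already modelled as a repeated measure. Gender belongs in the model because it is the randomisation factor, not for a material power gain.

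**What to change.** 1. In 6.4.1 and 6.4.3, delete the clause that uses baseline comparisons to judge whether covariates are needed. Baseline characteristics can still be described by arm.
2. In 6.4.4, replace N/A with: *All between-arm analyses of questionnaire outcomes adjust for the baseline value of that outcome, where one is collected, and for gender (the urn factor); other between-arm analyses adjust for gender.*
3. In 6.4.3.2, state how the estimating-equation model uses the intake score, so that it agrees with 6.4.4 and intake is not entered both as a covariate and as an outcome.

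The cost is wording plus one or two degrees of freedom. One dependency must be handled with it: Section 6.4.5 codes missing data as zero, and missing baseline values must not enter the adjusted model as zeros.
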